5.5 Duration of Therapy

In the absence of treatment delays due to adverse event(s), treatment may continue for up to 12 cycles (i.e. 12 months) if there is clinical benefit (i.e. PR or CR) after the first 6 cycles, (i.e. 6 months) or until one of the following criteria applies:

- Chronic GVHD or malignancy progression,
- Intercurrent illness that prevents further administration of treatment,
- Unacceptable adverse event(s) (see section 6.1)
- Patient decides to withdraw from the study, or
- General or specific changes in the patient's condition render the patient unacceptable for further treatment in the judgment of the investigator.

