9.1.2 Definition of Response to Therapy

1. Stable disease (SD) (no change in chronic GVHD) according to NIH consensus response criteria for a total of 1month [46]. This criteria is irrespective of any response obtained initially, prior to the month of stability.
2. Progressive Disease: This is defined as any one of the following:
 - Skin: Increase in NIH Skin Score by 1 or more points, except 0 to 1.
 - Eyes: Increase in NIH Eye Score by 1 or more points, except 0 to 1.
 - Mouth: Increase in NIH Modified Oral Mucosa Rating Score of 2 or more points.
 - Esophagus: Increase in NIH Esophagus Score by 1 or more points, except 0 to 1.
 - Upper GI: Increase in NIH Upper GI Score by 1 or more points, except 0 to 1.
 - Lower GI: Increase in NIH Lower GI Score by 1 or more points, except from 0 to 1.
 - Liver: Increase by 2x ULN ALT, alkaline phosphatase, and Total bilirubin.
 - Lungs: Decrease by 10% predicted absolute value of %FEV1. If PFTs not available, increase in NIH Lung Symptom Score by 1 or more points, except 0 to 1.
 - Joints and Fascia: Increase in NIH Joint and Fascia Score by 1 or more points or decrease in P-ROM score by 1 point for any site.
 - Global: Clinician overall severity score increases by 2 or more points on a 0 – 10 scale
3. Partial Response: This is defined as any one of the following:
 - Skin: Decrease in NIH Skin Score by 1 or more points
 - Eyes: Decrease in NIH Eye Score by 1 or more points
 - Mouth: Decrease in NIH Modified Oral Mucosa Rating Score of 2 or more points.
 - Esophagus: Decrease in NIH Esophagus Score by 1 or more points.
 - Upper GI: Decrease in NIH Upper GI Score by 1 or more points
 - Lower GI: Decrease in NIH Lower GI Score by 1 or more points.
 - Liver: Decrease by 50% ALT, alkaline phosphatase, and Total bilirubin.
 - Lungs: Increase by 10% predicted absolute value of %FEV1. If PFTs not available, decrease in NIH Lung Symptom Score by 1 or more points.
 - Joints and Fascia: Decrease in NIH Joint and Fascia Score by 1 or more points or increase in P-ROM score by 1 point for any site.

- Global: Clinician overall severity score decreases by 2 or more points on a 0 – 10 scale.
4. Complete Response: This is defined as any one of the following:
- Skin: NIH Skin Score 0 after previous involvement.
 - Eyes: NIH Eye Score 0 after previous involvement.
 - Mouth: NIH Modified Oral Mucosa Rating Score 0 after previous involvement.
 - Esophagus: NIH Esophagus Score 0 after previous involvement.

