 - Upper GI: NIH Upper GI Score 0 after previous involvement.
 - Lower GI: NIH Lower GI Score 0 after previous involvement.
 - Liver: Normal ALT, alkaline phosphatase, and Total bilirubin after previous elevation of one or more.
 - Lungs: Normal %FEV1 after previous involvement. If PFTs not available, NIH Lung Symptom Score 0 after previous involvement.
 - Joints and Fascia: Both NIH Joint and Fascia Score 0 and P-ROM score 25 after previous involvement by at least one measure.
 - Global: Clinician overall severity score 0.

Patients under categories 1 and 2 require the addition of other systemic treatment for chronic GVHD. These conditions should be attributable to chronic GVHD, with exclusion of other relevant causes in the differential diagnosis when applicable. The addition of other systemic treatment excludes the patient from the current clinical study.

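### Section 9.1.2 lets any single line make a patient a Complete Response and gives no rule for combining organs, so the descriptive six-month response table can overstate CR

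*Combined protocol and SAP*

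**What the plan says.** Section 9.1.2 sets out four categories. Three share one construction: "Progressive Disease: This is defined as any one of the following", "Partial Response: This is defined as any one of the following" and "Complete Response: This is defined as any one of the following". Each is followed by the same ten headings: skin, eyes, mouth, esophagus, upper GI, lower GI, liver, lungs, joints and fascia, and a clinician Global score. The last line of the CR list is "Global: Clinician overall severity score 0". Stable disease is defined differently, as no change "according to NIH consensus response criteria for a total of 1month".

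The section then applies the categories to patients: "Patients under categories 1 and 2 require the addition of other systemic treatment for chronic GVHD", where categories 1 and 2 are SD and PD. Section 5.5 allows treatment beyond six months "if there is clinical benefit (i.e. PR or CR) after the first 6 cycles" and lists "Chronic GVHD or malignancy progression" among the reasons to stop.

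Section 10.1.2 makes clinical response at six months a secondary endpoint and refers to 9.1.2 for its definition. Section 10.2 plans a table of PD, SD, PR and CR by organ and overall. No section says how organ results become an overall result, or which category prevails when more than one is met. Section 9.1 also uses the word response for FFS at six months; that is the primary endpoint and a separate matter.

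**The concern.** An overall Complete Response is normally understood to mean that the disease has cleared everywhere it was present. Here one cleared line is enough, whatever the other organs do. In multi-organ disease that is close to the opposite of what a reader of the results would assume. The same construction lets one patient satisfy categories that should exclude each other.

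At stake is the meaning of the CR row in a pilot that section 13 expects to inform larger trials, in a disease whose advanced stage section 2.1 describes as almost never responding to current treatment. Even one CR would attract attention, so it should be clear what it means.

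**Working it through.** The plan states no figure for this endpoint, so there is none to reproduce. The check is to apply the stated rule to simple cases.

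**Step 1: apply the lines.** Scores are baseline to month 6, and organs not shown are uninvolved. The last column uses the overall rule proposed under the fix.

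| Case | CR line met | PR line met | PD line met | As written | Overall rule |
|---|---|---|---|---|---|
| A: eyes 1 to 0, skin 3 to 3 | eyes | eyes | none | CR and PR | PR |
| B: skin 1 to 0, eyes 1 to 2 | skin | skin | eyes | CR, PR and PD | PD (mixed) |
| C: skin 1 to 0, only organ involved | skin | skin | none | CR and PR | CR |

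Case A is labelled CR with severe skin disease unchanged. Case B meets three categories at one visit. In case C the two rules agree on CR, because only one organ is involved. The problem therefore arises only in patients with two or more involved organs.

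**Step 2: do such patients exist?** Section 4.1.5 requires only one fibrotic manifestation. Section 2.1 says the disease can involve several organs, and section 10.1.2 names more than three involved sites as a possible prognostic factor. Multi-organ patients are expected, but their number is not given.

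**Step 3: size per patient.** With N = 12 (section 10.2), one mislabelled patient moves the CR rate by 1/12 = 8.3 percentage points, for example from 0/12 to 1/12.

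**Step 4: why the number mislabelled cannot be estimated.** Let k be the number of involved organs and c the chance that an organ clears. If organs are independent, CR as written has probability 1 − (1 − c)^k, and CR with every organ cleared has probability c^k. Neither c nor k is in the documents, so the values below are assumptions.

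| k | c | As written | All organs clear | Difference × 12 |
|---|---|---|---|---|
| 1 | any | c | c | 0 |
| 2 | 0.02 | 4.0% | 0.04% | 0.5 |
| 2 | 0.20 | 36% | 4% | 3.8 |
| 3 | 0.02 | 5.9% | under 0.01% | 0.7 |
| 3 | 0.20 | 48.8% | 0.8% | 5.8 |

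For k = 3 and c = 0.20: 1 − 0.8³ = 0.488, 0.2³ = 0.008, and 12 × 0.480 = 5.8. If organs within a patient tend to clear together, the gap narrows. The range runs from 0 to about 6 of 12 according to the assumptions chosen, so it shows the direction of the error but does not estimate its size.

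**The case against.** The best defence is that the nine organ lines give organ response and the Global line gives overall response. That fits the two-level table in section 10.2, and Appendix F, which lists organs and then a separate grade block. As a guess at intent it is reasonable, and that much stands. But the text does not say it. The Global line is one of ten alternatives under an any-one rule, and 9.1.2 and 5.5 apply the categories to whole patients.

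A second defence is that section 10.2 invokes NIH criteria, which might supply the rule. Section 10.2 gives no reference number, and section 10.1.2 points to 9.1.2. The only source cited in 9.1.2, for SD, appears in section 16 as a diagnosis and staging report. Its contents were not available for this review. Its title does not point to a rule for combining organ responses, and the plan does not import one.

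The points on consequence stand in full. The organ table would sit beside the overall one, so an uncleared organ would be visible. Change in NIH global score is a separate secondary endpoint. Clinical response is not among the objectives in section 1, and no test or go/no-go decision uses the CR count.

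A reader might also infer that the primary endpoint is compromised, because PD leads to added therapy and added therapy is an FFS failure. The documents do not support that. FFS does not use CR or PR, 5.5 treats the two alike, and 9.1.2 and 5.5 already act on progression, so a mixed patient is most naturally handled as PD. Nor do the documents support any particular number of false CRs.

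**Conclusion.** The concern holds for the overall response table. This is a stated rule that gives a wrong label, not merely missing detail: as written, clearing one of several involved organs is a CR, and the categories can overlap with no order of precedence. The size is 8.3 points on the CR rate per mislabelled patient, in a descriptive table of 12. How many patients would be affected is unknown and could be none. The conclusion rests on reading 9.1.2 literally and on at least some patients having more than one involved organ; it needs no assumed clearance rate. It should be fixed before the table is produced, but it does not threaten the primary analysis.

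**What to change.** State in 9.1.2 that the listed lines are organ-level definitions, and add an overall rule for the section 10.2 table:

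- **Overall PD:** any PD line is met. This takes precedence over PR and CR, and mixed responses are footnoted.
- **Overall CR:** every listed organ involved at baseline meets its CR line, and no PD line is met. The Global line alone does not establish overall CR while an involved organ has not cleared.
- **Overall PR:** at least one PR or CR line is met, no PD line is met, and the patient is not a CR. CR lines must be included because a mouth score going from 1 to 0 meets the CR line but not the two-point PR line.
- **SD:** all others, for tabulation only. The existing one-month SD trigger for added therapy is unchanged.

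The rule keeps the plan's own thresholds, including the exception for 0 to 1 in most PD lines; joints and fascia has no such exception. Vaginal disease qualifies a patient under 4.1.5 but has no line in 9.1.2, so a footnote should say that overall CR covers the nine listed organs.

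The cost is wording. The organ items are on the Appendix F flowsheet and in the scheduled chemistries, and lung function is repeated in patients with lung involvement. The site should confirm that the range-of-motion and 0–10 clinician scores are on record. A patient who moves from CR to PR keeps eligibility for extension under 5.5. The downside is a lower reported CR rate, and a CR+PR rate lower by any mixed patients.

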5.6 Duration of Follow Up

Patients will be followed for a total of 6 months after removal from study treatment or until death, whichever occurs first. Patients removed from study for unacceptable adverse event(s) will be followed until resolution or stabilization of the adverse event.

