5.7 Criteria for Removal from Study

Patients will be removed from study when any of the criteria listed in [Section 5.5](#) applies. The reason for study removal and the date the patient was removed must be documented in the Case Report Form. In addition, early stopping criteria are defined in Section 9.

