9.1.1 Failure Free Survival Definition

FFS is defined as being alive and:

- No relapse of malignancy
- No addition of any other systemic treatment for chronic GVHD
- Steroid dose at 6 months \leq 0.2 mg/kg/day PDE

The need for addition of therapy while on GDC-0449 is one of the criteria for failure, and consequently the patient will be taken off study. In order to minimize differences in practice that might impact the primary endpoint, we established minimal indispensable criteria to initiate additional immunosuppressive therapy during the first six months of GDC-0449 treatment.

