10.1.1 Primary Endpoint

- FFS at 6 months after initiation of therapy with GDC-0449
FFS is defined as absence of NRM, no recurrent malignancy, steroid dose at 6 months ≤ 0.2 mg/kg/d of PDE, and no addition of new systemic treatment for chronic GVHD (Adapted from [45]). Criteria for addition of new systemic treatment for chronic GVHD are defined as per [section 9.0](#).

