10.2 Sample Size/Accrual Rate/Other Statistical Considerations

Sample size: 12 patients. Accrual rate: 1-2 patients monthly.

This is a pilot study that will include 12 patients. FFS, the primary endpoint, will be evaluated using the Kaplan-Meier method. The impact of different covariates on FFS will be analyzed using descriptive statistics, t-test, and Fisher's exact test where applicable. Differences in NIH scores will be analyzed using Wilcoxon signed-rank test. Differences in biomarkers will be assessed using Wilcoxon rank-sum test.

Overall clinical response (PD, SD, PR, CR) according to NIH criteria will be tabulated and described based on organ response and overall response.

The proportion of subjects who experience adverse events and serious adverse events will be summarized descriptively; no inferential tests will be performed.

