All adverse events will be treated appropriately. Such treatment may include changes in study drug treatment as listed in the dose modification section of this protocol (see section 6 for guidance). Once an adverse event is detected, it should be followed until its resolution, or until the end of the follow-up period (6 months after removal from study treatment or until death, whichever occurs first) and assessment should be made at each visit (or more frequently, if necessary) of any changes in severity, the suspected relationship to the study drug, the interventions required to treat it, and the outcome.

Information about common side effects already known about the investigational drug is described in the Drug Information (section 3) and the most recent Investigator Brochure. This information will be included in the patient informed consent and will be discussed with the patient during the study as needed.

All adverse events will be immediately recorded in the patient research chart.

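### Sections 5.7, 9.1.1 and 9.1.2 take failing patients off study while 5.6 and 8.3 follow them for 6 months, so the completeness of one-year OS, NRM and relapse depends on which wording is followed

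*Combined protocol and SAP*

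**What the plan says.** **Wording that ends participation**

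- Section 5.7: "Patients will be removed from study when any of the criteria listed in" Section 5.5 applies. Those criteria include progression of chronic GVHD or of the malignancy, intercurrent illness, unacceptable adverse events, patient withdrawal and investigator judgment.
- Section 9.1.1: needing additional therapy while on GDC-0449 is a failure criterion, and "consequently the patient will be taken off study".
- Section 9.1.2: stable disease and progressive disease both call for added systemic GVHD treatment, and "The addition of other systemic treatment excludes the patient from the current clinical study".

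**Wording that continues observation**

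- Section 5.6: "Patients will be followed for a total of 6 months after removal from study treatment or until death, whichever occurs first". For patients removed from study because of unacceptable adverse events, it adds that they "will be followed until resolution or stabilization of the adverse event".
- Section 8.3 and a footnote to the Section 7 calendar: visits every 3 months for 6 months after GDC-0449 stops, with no exception for treatment failure.
- Section 14.1.1: an adverse event is followed to resolution "or until the end of the follow-up period (6 months after removal from study treatment or until death, whichever occurs first").

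**What the analysis needs**

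- The primary endpoint in Section 10.1.1 is "FFS at 6 months after initiation of therapy with GDC-0449".
- Section 10.1.2 requires NRM, relapse, FFS and OS at one year, and NIH global score change at 6 and 12 months.
- Section 10.2 names Kaplan-Meier for FFS only. It gives no censoring or competing-risk rule for OS, NRM or relapse.

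**The concern.** Two coordinators could each comply with the protocol and collect different data. One closes the record when a patient progresses or starts new therapy. The other sees the same patient at 3 and 6 months after the last dose and records a death or relapse.

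Under the first reading, observation stops at events that plausibly precede death: GVHD progression, intercurrent illness and toxicity. If mortality is higher after those events, censoring there is informative, and OS is overstated and NRM understated. Section 9.1.2 applies to stable as well as progressive disease, so removal may not be rare. With 12 patients, each unseen death is one twelfth of the sample.

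The primary endpoint is exposed only in part. Added therapy and relapse are themselves FFS events, so nothing that happens after them changes FFS. Toxicity and intercurrent illness are not FFS events. A patient removed for either before month 6 could have a later death, relapse, added treatment or month-6 steroid dose that nobody records.

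**Working it through.** The plan gives no figure to reproduce. Section 10.2 says only "This is a pilot study that will include 12 patients" and gives no precision target. The check is therefore of observation time, followed by an illustration of size.

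**1. Observation time.** For a patient whose treatment stops at month t, observation ends at t under the off-study reading and at t + 6 under 5.6 and 8.3. Months of the one-year window lost are 12 − t and max(0, 6 − t).

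| Stop at month t | Off-study reading | 5.6 / 8.3 |
|---|---|---|
| 1 | 11 | 5 |
| 3 | 9 | 3 |
| 5 | 7 | 1 |
| 6 | 6 | 0 |
| 8 | 4 | 0 |
| 10 | 2 | 0 |

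The two rules differ by up to 6 months of the one-year window. For patients who stop before month 6, neither rule reaches one year.

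**2. Bounds without a model.** Assume k of 12 patients are removed, their vital status is then lost, and all others live. One-year OS is then known only to lie between (12 − k)/12 and 100%: 75-100% for k = 3, 67-100% for k = 4, 50-100% for k = 6 and 33-100% for k = 8.

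**3. Illustration with a model.** All inputs here are assumptions; the documents supply none of them.

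- A proportion p = 50% or 65% is removed by 6 months at a constant hazard: λ = −ln(1 − p)/6 = 0.1155 or 0.1750 per month.
- The death hazard is h before removal and r·h after it.
- True one-year OS is 80%, so 12 × 0.20 = 2.4 deaths are expected.
- OS is censored at removal.

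With d = h + λ − r·h, one-year OS = exp(−12(h + λ)) + (λ/d)·[exp(−12·r·h) − exp(−12(h + λ))]. Set this to 0.80 and solve for h. Then:

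- Kaplan-Meier OS censored at removal = exp(−12h)
- Deaths seen = 12·[h/(h + λ)]·[1 − exp(−12(h + λ))]

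| p | r | h per month | Kaplan-Meier OS | Deaths seen of 2.4 | Deaths unseen |
|---|---|---|---|---|---|
| 50% | 1 | 0.01860 | 80.0% | 1.33 | 45% |
| 50% | 3 | 0.00985 | 88.9% | 0.73 | 69% |
| 50% | 5 | 0.00675 | 92.2% | 0.51 | 79% |
| 65% | 1 | 0.01860 | 80.0% | 1.04 | 57% |
| 65% | 3 | 0.00868 | 90.1% | 0.50 | 79% |
| 65% | 5 | 0.00569 | 93.4% | 0.33 | 86% |

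With equal hazards (r = 1) OS is unbiased, but 45-57% of deaths still go unseen.

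**4. Does 5.6 alone repair it?** In the same model with r = 3 to 5, following every patient for 6 months after removal sees 1.8 to 1.9 of the 2.4 deaths and misses 19-26%. Kaplan-Meier OS is then 81-82% against the true 80%. That is most of the repair, but not all of it.

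**The case against.** The strongest reply is that 'off study' is loose wording for 'off treatment'. Much of the text supports it. Section 5.6 itself follows patients described as removed from study for adverse events. Section 5.7 takes its triggers from a section on duration of therapy. Section 9.1.1 speaks of patients still on the drug. The medication diary (Appendix D) asks for the date of removal from study beside the treatment start date and capsule count. Post-treatment follow-up of 6 months appears in 5.6, 8.3, the calendar footnote and 14.1.1. This stands as a plausible account of intent. It does not settle the matter: 5.6 says so only for adverse events, neither term is defined, and the sentence in 9.1.2 is hard to read as merely stopping a drug.

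Four stronger readings are tempting, and the documents do not support them.

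- *That the plan censors OS at treatment failure.* It states no OS censoring rule; censoring at removal is an assumption of the illustration.
- *That OS will be overstated by 9 to 13 points.* The removal rate, the true OS and the hazard ratio have no anchor in the documents. FFS failure also includes a month-6 steroid dose above 0.2 mg/kg/day, which is not a listed removal trigger, so an FFS failure rate cannot stand in for the removal rate.
- *That the primary endpoint is generally biased.* FFS is unaffected where added therapy or relapse is the reason for removal, and a relapse that triggers removal is itself seen. The exposure is limited to removals that are not FFS events.
- *That all outcomes are captured if 5.6 is followed.* Follow-up to t + 6 falls short of one year for anyone who stops before month 6.

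The mismatch between 5.6 and 14.1.1 on toxicities still open at 6 months is real but narrow, and it does not bear on OS or NRM bias.

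**Conclusion.** The point holds as an inconsistency in the current text with a real consequence for the secondary one-year endpoints. Followed literally, the off-study sentences leave deaths and later relapses unobserved after GVHD progression, intercurrent illness, toxicity or added therapy. One-year OS, NRM and relapse, and the 12-month NIH score, would be incomplete. OS and NRM would probably look too favourable; that direction depends on mortality being higher after removal, and no separate NRM calculation was made.

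What needs no clinical assumption is the 6 to 11 months of the one-year window lost when a patient stops in the first 6 months, against 0 to 5 under 5.6 and 8.3. The 89-93% OS and the 69-86% of deaths unseen show possible scale only, under the assumptions listed. This should be corrected, but it does not undermine the primary endpoint apart from patients removed before month 6 for reasons that are not FFS events.

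**What to change.** 1. In 5.7, 9.1.1 and 9.1.2, replace the three off-study phrases with 'removed from study treatment'. The criteria for stopping treatment stay as they are.
2. State that these patients remain in follow-up, unless consent is withdrawn, for vital status, relapse, cause of death and added therapy, and up to month 6 for steroid dose. Follow-up runs to the later of 12 months from first dose and 6 months after stopping treatment, because 5.6 alone does not reach one year for patients who stop before month 6.
3. In Section 10, state that OS, NRM and relapse are not censored at treatment failure.
4. Separately, reconcile 5.6 and 14.1.1 on how long toxicities still open at 6 months are followed.

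The cost is protocol wording plus a few extra vital-status contacts for early stoppers. The visits in 5.6 and 8.3 are already scheduled. Depending on how item 4 is settled, a few patients may need adverse-event follow-up beyond 6 months.
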